5.1.1 Retesting During Screening Period

Retesting of laboratory parameters and/or other assessments within any single Screening period will be permitted (in addition to any parameters that require a confirmatory value).

Any new result will override the previous result (i.e. the most current result prior to Randomization) and is the value by which study inclusion will be assessed, as it represents the subject's most current, clinical state.

Laboratory parameters and/or assessments that are included in [Table 5.1-2](#), Screening Procedural Outline may be repeated during the Screening period in an effort to find all possible well-qualified subjects. Consultation with the Medical Monitor may be needed to identify whether repeat testing of any particular parameter is clinically relevant.

5.2 Study Materials

BMS will supply the sites with the following materials:

- Electronic CRFs
- BMS SAE electronic CRF Form
- BMS Pregnancy Surveillance Form
- Adjudication binder and worksheets
- Mandatory Subject diary for study medication. The date of doses should be completed daily by the subject/ parent or study staff
- Laboratory manuals
- Study Reference materials

5.3 Safety Assessments

Safety Assessments will include AE reporting as well as bleeding events assessment.

The procedures described in the sections below will be completed to ensure subject's safety.

5.3.1 Bleeding Assessment

Bleeding definitions are based on the Perinatal and Paediatric Haemostasis Subcommittee of International Society on Thrombosis and Haemostasis (ISTH) criteria,²⁹ and are described as follows:

Major bleeding is defined as bleeding that satisfies one or more of the following criteria: (i) fatal bleeding; (ii) clinically overt bleeding associated with a decrease in Hgb of at least 20 g/L (2 g/dL) in a 24 hour period; (iii) bleeding that is retroperitoneal, pulmonary, intracranial, or otherwise involves the central nervous system; and (iv) bleeding that requires surgical intervention in an operating suite (including interventional radiology).

Clinically relevant non-major (CRNM) bleeding is defined as bleeding that satisfies one or both of the following: (i) overt bleeding for which a blood product is administered and which is

not directly attributable to the patient’s underlying medical condition and (ii) bleeding that requires medical or surgical intervention to restore hemostasis, other than in an operating suite.

Minor bleeding: is defined as any overt or macroscopic evidence of bleeding that does not fulfill the above criteria for either major bleeding or CRNM bleeding.

Menstrual bleeding resulting in a medical consultation and/or intervention will be classified as a minor bleeding event.

All bleeding events and their supporting documentation **MUST** be sent for adjudication.

5.3.2 Treatment Guidelines for Bleeding / Suspected Bleeding

Subjects with bleeding or suspected bleeding should undergo confirmatory laboratory or other testing as indicated clinically (e.g., Ultrasound, Computer Tomography [CT], Magnetic Resonance Imaging [MRI]). The date and time of the onset of the bleeding event will be recorded on the CRF. The following routine measures may be considered:

- Delay the next dose of study drug or discontinue study medication if indicated
- Provide fluid resuscitation and blood transfusion as indicated
- Provide fresh frozen plasma (FFP) or general hemostatic measures as indicated

[figure not shown]
Note: There is no specific reversal agent for apixaban for use in infants and children.

Table 5.3.2-1 provides recommendations for the treatment of bleeding or suspected bleeding. The specific treatment for bleeding is left to the discretion of the investigator and/or the treating physician based on the medical status of the subject and/or institutional policies.

| Table 5.3.2-1: Treatment Guidelines for Bleeding / Suspected Bleeding | |
|--|---|
| Minor Bleeding | Apixaban may or may not be held based on an individualized benefit-risk assessment |
| Clinically Significant Bleeding / Clinically Relevant Non-Major Bleeding | 
Apixaban should be held if subject meets criteria outlined in section 3.5. Hold apixaban for clinically significant bleeding. Identify the source and institute local measures to stop the bleeding.
 
 • Perform laboratory test monitoring (e.g., hemoglobin, INR, aPTT, platelet count, anti-FXa activity). • Apixaban may be best monitored using an anti-FXa assay rather than the more standard coagulation tests (e.g., INR, aPTT) which are less sensitive to apixaban. • If bleeding occurs within 6 hours after apixaban administration consider administration of activated charcoal oral solution to reduce apixaban plasma exposure. • Consider appropriate symptomatic treatment (e.g., mechanical compression, surgical intervention, fluid replacement and hemodynamic support, blood product or component transfusion) • For bleeding that does not respond to local measures, consider administration of FFP as a supportive measure, recognizing that FFP does not reverse the anticoagulant effects of apixaban |

| Table 5.3.2-1: Treatment Guidelines for Bleeding / Suspected Bleeding | |
|--|---|
| Life Threatening Bleeding / Major Bleeding | 
Apixaban should be held for all life threatening bleeding.
 
• Administration of recombinant Factor VIIa may be considered, however, there is no experience with this agent in apixaban-treated patients. Its effectiveness for counteracting the effects of apixaban is not known.• Activated prothrombin complex concentrate (aPCC) or prothrombin complex concentrate (PCC, also referred to as factor IX concentrate) are other procoagulants that may be considered, but considering the variety of formulations available and the complexity of dosing, the decision to employ aPCC or PCC should be made by an experienced clinician with careful evaluation of the risks and benefits.• If bleeding occurs within 6 hours after apixaban administration activated charcoal oral solution administration may be considered in order to reduce apixaban plasma exposure. |

Please follow the product label or institutional protocol for the treatment of bleeding associated with VKA or LMWH.

5.3.3 Laboratory Assessments

Blood samples will be obtained on selected visits of clinical laboratory evaluations as outlined in [Section 5.1](#) ([Table 5.1-1](#) and [Table 5.1-2](#) - Flow chart/ Time and Events Schedule). [Appendix 1](#)

outlines the blood sampling schedule, including total amounts of blood drawn. A local laboratory should perform the laboratory tests and will provide reference ranges for these tests. The following laboratory tests are required for this study, and should be analyzed by the local laboratory: CBC, ALT, AST, and total and conjugated bilirubin, serum creatinine (estimated GFR), aPTT, INR (coagulation tests and serum creatinine at screen only), and serum or urine pregnancy test when applicable. Special kits will be provided for the PK, anti-Xa activity, [REDACTED] and chromogenic Factor X samples. There will be detailed instructions in a laboratory manual for specimen collection, processing, storage, and shipment. INR levels for subjects receiving VKA will either be done using the local laboratories or collected on a home monitoring device between visits and recorded in the patient's diary. Anti-Xa levels for subjects receiving LMWH will be done using the local laboratories.

5.3.4 Pregnancy Tests

For WOCBP, a serum or urine pregnancy test should have a minimum sensitivity of 25 IU/L or equivalent units of β HCG. All on-study pregnancy testing should follow the schedule detailed in [Table 5.1-1](#).

5.3.5 Creatinine Clearance

Based on the results of the enrollment visit clinical laboratory tests, eGFR will be estimated based on the Schwartz formula (See [Table 5.1-1](#) for timing of assessments and [Appendix 5](#) for eGFR assessment).

Inadequate Renal Function is defined as < 30% of normal for age and size as determined by the Schwartz formula³⁷ [$eGFR \text{ (ml/min/1.73m}^2\text{)} = 0.413 \times (\text{height (cm)} / \text{serum creatinine (mg/dl)})$]. If serum creatinine concentration is measured in SI units (umoles/L), divide this number by the conversion factor of 88.4 to get the SI units (mg/dl) before inserting into the Schwartz formula to calculate eGFR]. Subjects are required to have an eGFR > 30% of normal for age, gender, and height to be enrolled in the study ([Appendix 5](#)).

5.3.6 Physical Examination

[figure not shown]
A full physical examination should include general appearance, head, eyes, ears, nose, throat, neck, cardiovascular, lungs, abdomen, lymph nodes, extremities, neurological, skin, musculoskeletal, vital signs (heart rate, respiratory rate, blood pressure and temperature), height and weight.

A targeted physical examination should include any organ systems pertinent to the subject's signs, symptoms, or AES, such as assessment of signs of thromboembolism or bleeding.

Only Investigators licensed to conduct physical examinations and who are listed on the Delegation of Authority Form are approved to perform physical examinations.

5.3.7 Imaging Assessment for the Study

[REDACTED]

Routine mandatory images for thromboembolic events are not required for the study. However, any clinical, radiologic and catheter evaluations prompted by clinical suspicion of any thromboembolic events, bleeding or death can be performed at the discretion of the site principal investigator and/or treating clinician; information from these visits and findings will be captured for study analysis.

5.4 Efficacy Assessments

This is a safety and PK study, and there is no primary efficacy assessment in this study. The secondary assessments include any thromboembolic events (intra-cardiac, shunt, inside Fontan pathway, PE, stroke, other venous or arterial thromboembolic events) detected by imaging or clinical diagnosis, and thromboembolic event-related death. Thromboembolic event-related death and thromboembolic events will be adjudicated by a blinded, independent EAC.

5.5 Pharmacokinetic and Pharmacodynamic Assessments

Samples for PK and PD (Chromogenic FX assay) will be taken in subjects receiving apixaban only. Chromogenic FX assay which measures (apparent) FX level will be used to assess endogenous FX level at baseline and inhibition of FXa by apixaban. In addition, anti-FXa activity, which uses exogenous FXa and apixaban calibrators will be measured in subjects receiving apixaban to assess their plasma apixaban levels. PK samples may be analyzed for the concentration of apixaban in a timely manner during the study, if needed. There will be special kits and detailed instructions in a laboratory manual provided for specimen collection, processing, storage, and shipment. For subjects undergoing surgery and possibly getting a transfusion, the PK/PD and chromogenic Fx samples should be drawn before the transfusion or surgery or at least a week after surgery.

[Table 5.5-1](#), [Table 5.5-2](#), [Table 5.5-3](#), and [Table 5.5-4](#) summarizes the sampling collection schedule for children ≥ 1 to < 18 years of age, infants 3 months to < 1 years of age, infants 28 days to < 3 months using whole blood, and infants 28 days to < 3 months using dried blood spot (DBS) respectively (for PK, PD ). (See [Appendix 1](#) for additional information including total amount of blood drawn during the study). Attempts should be made to coordinate blood sampling with the blood draw for safety labs.

Table 5.5-1: Sampling Schedule for PK, PD [REDACTED] for children (1 to < 18 years of age)

| Procedure | Subjects | Screening Day -21 to Day 1 | Day 1 ^{a, b} | Week 2 ^b ± 3 days | Month 3 ^b ± 2 weeks | Month 6 ^{b,c} ± 2 weeks | Whole Blood Volume |
|--|--------------------------|----------------------------|--|---------------------------------|-----------------------------------|-------------------------------------|--|
| Serial PK and Anti-FXa activity ^c | Subjects taking Apixaban | | 4 hr (3-8 hr) | Pre-dose | 2 ± 1 hr Post dose | Pre-dose | 2 ml sample for PK and anti-FXa combined |
| Chromogenic FX ^c | Subjects taking Apixaban | | Prior to first dose ^d and 4 hr (3-8 hr) ^a | | 2 ± 1 hr Post dose | Pre-dose | 1.4 mL / sample |

^a The Day 1 post dose 4 hr (3-8 hr) sample should be taken 3-8 hr after the first apixaban dose. For those subjects on VKA prior to study entry who are randomized to apixaban, and have to wait for their INRs to be below 2 before starting apixaban, the Day 1 post dose 4 hr (3-8 hr) sample should be postponed and only be done 3-8 hr after the subject has taken their first dose of apixaban.

^b For subjects undergoing surgery and possibly getting a transfusion, the PK/PD and chromogenic Fx [REDACTED] samples should be drawn before the transfusion or surgery or at least a week after surgery

^c For subjects who discontinue before the month 6 visit, blood samples will be taken at the end of the treatment discontinuation.

^d Blood samples can be taken any time prior to the first dose of study drug at randomization (Day1).

Table 5.5-2: Sampling Schedule for PK and PD for children 3 months to < 1 years of age

| Procedure | Subjects | Screening Day -21 to Day 1 | Day 1 ^{a,b} | Week 2 ^b ± 3 days | Month 3 ^b ± 2 weeks | Month 6 ^{b,c} ± 2 weeks | Whole Blood Volume |
|---|-----------------------------|----------------------------------|--|---------------------------------|-----------------------------------|-------------------------------------|---|
| Serial PK and Anti-FXa activity ^c | Subjects taking Apixaban | | 4 hr (3-8 hr) | Predose | 2 ± 1 hr Post dose | Predose | 1.4 mL sample for PK and anti-FXa combined |
| Chromogenic FX ^c | Subjects taking Apixaban | | Prior to first dose ^d and 4 hr (3-8 hr) ^a | | 2 ± 1 hr Post dose | Predose | 1.4 mL / sample |

^a The Day 1 post dose 4 hr sample should be taken 3-8 hr after the first apixaban dose. For those subjects on VKA prior to study entry who are randomized to apixaban, and have to wait for their INRs to be below 2 before starting apixaban, the Day 1 post dose 4 hr (3-8 hr) sample should be postponed and only be done 3-8 hr after the subject has taken their first dose of apixaban

^b For subjects undergoing surgery and possibly getting a transfusion, the PK/PD and chromogenic Fx [REDACTED] samples should be drawn before the transfusion or surgery or at least a week after surgery

^c For subjects who discontinue before the month 6 visit, blood samples will be taken at the end of the treatment discontinuation.

^d Blood samples can be taken any time prior to the first dose of study drug at randomization (Day1).

Table 5.5-3: Sampling Schedule for PK and PD using serum samples for children 28 days to < 3 months of age

| Procedure | Subjects | Day 1 ^{a, b} | Week 2 ^b ± 3 days | Month 3 ^b ± 2 weeks | Whole Blood Volume |
|-------------------|--------------------------|----------------------------------|---------------------------------|-----------------------------------|--|
| Serial PK | Subjects taking Apixaban | 4 hr (3-8 hr) | Pre-dose | 2 ± 1 hr Post dose | 1.4 ml sample for PK and anti-FXa combined |
| Anti-FXa activity | Subjects taking Apixaban | | | 2 ± 1 hr Post dose | |
| Chromogenic FX | Subjects taking Apixaban | Prior to first dose ^c | | 2 ± 1 hr Post dose | 1.4 mL / sample |

a The Day 1 post dose 4 hr (3-8 hr) sample should be taken 3-8 hrs after the first apixaban dose. For those subjects on VKA prior to study entry who are randomized to apixaban, and have to wait for their INRs to be below 2 before starting apixaban, the Day 1 post dose 4 hr (3-8 hr) sample should be postponed and only be done 3-8 hr after the subject has taken their first dose of apixaban.

b For subjects undergoing surgery and possibly getting a transfusion, the PK/PD and chromogenic FX [REDACTED] samples should be drawn before the transfusion or surgery or at least a week after surgery

c Blood samples can be taken any time prior to the first dose of study drug at randomization (Day1).

Table 5.5-4: Sampling Schedule for PK and PD using dried blood spot (DBS) sampling for children 28 days to < 3 months of age^d

| Procedure | Subjects | Day 1 ^{a, b, c, d} | Week 2 ^b ± 3 days | Month 3 ^b ± 2 weeks | Whole Blood Volume |
|------------------------|--------------------------|----------------------------------|---------------------------------|-----------------------------------|---|
| Serial PK ^c | Subjects taking Apixaban | 4 hr (3-8 hr) | Predose | 2 ± 1 hr Post dose | 1.4 ml serum sample for PK at Day 1 only |
| Anti-FXa activity | Subjects taking Apixaban | | | 2 ± 1 hr Post dose | PK and anti-FXa sample combined |
| Chromogenic FX | Subjects taking Apixaban | Prior to first dose ^c | | 2 ± 1 hr Post dose | 60-80 uL for PK DBS samples at Day 1, Week 2, and Month 3 |
| | | | | | 1.4 mL / sample |

[figure not shown]
a The Day 1 post dose 4 hr (3-8 hr) sample should be taken 3-8 hrs after the first apixaban dose. For those subjects on VKA prior to study entry who are randomized to apixaban, and have to wait for their INRs to be below 2 before starting apixaban, the Day 1 post dose 4 hr (3-8 hr) sample should be postponed and only be done 3-8 hr after the subject has taken their first dose of apixaban.

b For subjects undergoing surgery and possibly getting a transfusion, the PK/PD and chromogenic FX [REDACTED] samples should be drawn before the transfusion or surgery or at least a week after surgery

^c Blood samples can be taken any time prior to the first dose of study drug at randomization (Day1).

^d A single PK serum sample will be collected at the Day 1 visit only for subjects using DBS collection

^e Dried blood spot (DBS) may be used as an alternative collection method for PK in subjects under the age of 3 months at the time of randomization. If an investigator opts to use DBS, it must be used for all PK collection points.

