3.3.1 Inclusion Criteria

1. Signed Written Informed Consent

- a) Signed written informed consent obtained from subject's legally acceptable representative (parents or legal guardians) according to local regulations, and if the subject is mentally capable and assent is required locally, assent from the subject

2. Target Population

- a) Congenital or acquired heart diseases requiring chronic anticoagulation for thromboprophylaxis (e.g., single ventricle physiology including all 3 stages of palliation, dilated cardiomyopathy, Kawasaki disease with coronary aneurysms, and pulmonary hypertension)

Note: subjects with previous history of thromboembolic events greater than 6 months prior to enrollment are eligible, provided that there is evidence (by previously obtained clinical imaging data) for thrombus stability or resolution.

- b) Eligible subjects include those who newly start anticoagulants and those who are currently on VKA or LMWH or other anticoagulants for thromboprophylaxis
- c) Able to tolerate enteral medication (eg, by mouth, NG tube, or G-tube)
- d) Subject re-enrollment: This study permits the re-enrollment of a subject that has discontinued the study as a pre-treatment failure (ie, subject has not been randomized / has not been treated). If re-enrolled, the subject must be re-screened and re-consented
- e) Subjects 28 days to < 3 months must be able to tolerate oral/NGT/GT feeds for at least 5 days prior to randomization

3. Age and Reproductive Status

- a) Males and Females, 28 days to < 18 years of age, inclusive
- b) Women of childbearing potential (WOCBP) must have a negative serum or urine pregnancy test (minimum sensitivity 25 IU/L or equivalent units of HCG) within

24 hours prior to the start of study drug. An extension up to 72 hours is permissible in situations where pregnancy test results cannot be obtained within the standard 24 hour window

- c) Women must not be breastfeeding
- d) WOCBP must agree to follow instructions for method(s) of contraception for the duration of treatment with apixaban plus 5 half-lives of the drug (2 days) plus 30 days (duration of ovulatory cycle) for a total of 32 days post-treatment completion. For VKA and LMWH, please follow the local product label for instructions on contraception.
- e) Not applicable as per amendment 03
- f) Not applicable as per amendment 03

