Use of VKA or LMWH will follow the local standard of care that is aligned with the ACCP guidelines. The dose of VKA is recommended to be titrated to achieve a target international normalized ratio (INR) of 2.0 to 3.0, and the dose of LMWH is recommended to target an anti-Xa level between 0.5 and 1.0 units/mL. Exact targets may vary by condition and local standard of care. All INR (for subjects taking VKA) and anti-Xa (for subjects taking LMWH) values obtained during the study period per SOC will be recorded at each study visit. Patient diaries will be used to record study drug administration.

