4.5.3 Converting from or to Apixaban

Switching from VKA to apixaban: VKA should be discontinued and apixaban started when the INR is below 2.0.

Switching from apixaban to VKA: apixaban may affect INR, so that INR measurements during co-administration with VKA may not be useful for determining the appropriate dose of VKA. If continuous anticoagulation is necessary, discontinue apixaban and begin both a parenteral anticoagulant and VKA at the time the next dose of apixaban would have been taken, discontinuing the parenteral anticoagulant when the INR reaches an acceptable range per institutional standards.

Switching between apixaban and anticoagulants other than VKA: discontinue one being taken and begin the other at the next scheduled dose.

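### In children switched to apixaban, the Day 1 sampling rules can let VKA effect into baseline factor X and may let LMWH activity into the Day 1 anti-FXa reading.

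*Combined protocol and SAP*

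**What the plan says.** Section 3.3.1 admits children with anticoagulant exposure: "Eligible subjects include those who newly start anticoagulants and those who are currently on VKA or LMWH or other anticoagulants for thromboprophylaxis". PD, by chromogenic FX and anti-FXa activity, is a secondary objective (Section 1.3.2).

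Section 5.5 gives the two assays different jobs:
- "Chromogenic FX assay which measures (apparent) FX level will be used to assess endogenous FX level at baseline and inhibition of FXa by apixaban".
- The anti-FXa assay, "which uses exogenous FXa and apixaban calibrators", is read as the plasma apixaban level.

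On timing, the footnotes to the Section 5.5 tables treat the two Day 1 samples differently:
- Pre-dose FX: "Blood samples can be taken any time prior to the first dose of study drug at randomization (Day1".
- In children who come from VKA and must wait for a lower INR, the Day 1 post-dose "sample should be postponed and only be done 3-8 hr after the subject has taken their first dose of apixaban".

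The FX row of Table 5.1-1 lists both samples and likewise moves only the post-dose one.

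On switching, Section 4.5.3 starts apixaban after VKA once INR is below 2.0. For anticoagulants other than VKA the instruction is to "discontinue one being taken and begin the other at the next scheduled dose". Section 4.5 itself uses anti-Xa as the measure of LMWH effect: "the dose of LMWH is recommended to target an anti-Xa level between 0.5 and 1.0 units/mL". No pre-dose anti-FXa sample appears in any schedule.

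**The concern.** A baseline FX value serves its stated purpose only if it reflects the child's own factor X. A before/after pair measures apixaban only if nothing else changes between the two draws. For a child who waits for INR to fall, the footnotes fix the post-dose draw to the deferred first dose but leave the pre-dose draw free to happen at the randomization visit, while INR is still in range. The pair can then straddle the loss of VKA effect. If VKA lowers FX, the rise in FX as VKA wears off offsets apixaban's inhibition.

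The LMWH issue is a different mechanism on a different assay. A sample taken 3-8 h after an immediate switch may hold LMWH activity as well as apixaban, and apixaban calibrators would report the sum as apixaban.

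At stake is the description of PD: the FX effect, and the relation between concentration and anti-FXa. The same tables already guard these samples against transfusion and surgery, so protecting them from an outside influence is not new to the design. They do not guard against the prior anticoagulant.

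**Working it through.** **The plan's own count.** Section 8.1 expects approximately 533 PK/PD samples. 200 × 2/3 × 4 visits (Day 1, Week 2, Month 3, Month 6) = 533.3, and 133 × 4 = 532, so the figure reproduces. In children 3 months or older, Day 1 is one of four anti-FXa time points (25%).

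**What is assumed.** The protocol does not say that VKA lowers FX or by how much, how long the INR wait lasts, the share of VKA or LMWH switchers, the LMWH dosing interval, or LMWH kinetics. All values below are assumptions, shown as ranges.

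**1. Day 1 FX pair after VKA.** Let b be FX at the pre-dose draw and r be FX at the post-dose draw before apixaban's effect, both as fractions of the untreated level. Let i be the true inhibition. The observed post/pre ratio is r(1 - i)/b. With i = 0.30:
- both draws around the same first dose, r = b: ratio 0.70, which is correct
- b = 0.50, r = 0.70: 0.70 × 0.70/0.50 = 0.98, apparently almost no inhibition
- b = 0.30, r = 0.80: 0.80 × 0.70/0.30 = 1.87, an apparent rise

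**2. Month 3 and Month 6 against the same baseline.** VKA effect has gone, so r = 1 and apparent inhibition is 1 - (1 - i)/b. With i = 0.40:
- b = 1.0: 40%
- b = 0.8: 1 - 0.6/0.8 = 25%
- b = 0.6: 1 - 0.6/0.6 = 0%
- b = 0.4: 1 - 0.6/0.4 = -50%

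If half the apixaban arm came from VKA, the group mean would be 0.5 × 25% + 0.5 × 40% = 32.5% at b = 0.8. It would be 20% at b = 0.6 and -5% at b = 0.4, against a true 40%.

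**3. Day 1 anti-FXa after LMWH.** Assume an LMWH peak 4 h after its dose and a half-life of 3-7 h. The fraction of peak left when sampled s hours after the first apixaban dose is 2^(-(interval + s - 4)/half-life), with s from 3 to 8 h.
- 12 h interval: 2^(-16/3) = 0.025 to 2^(-11/7) = 0.336. On a peak of 0.5-1.0 units/mL this is about 0.01 to 0.34 units/mL.
- 24 h interval: 2^(-28/3) = 0.002 to 2^(-23/7) = 0.103, or about 0.001 to 0.10 units/mL.

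The documents give no conversion from these units to a reading on apixaban calibrators, so the shift in apparent apixaban level cannot be stated.

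**What lies outside the problem.**
- Apixaban concentration is measured by LC-MSMS (Section 8.4.4).
- Infants under 3 months have no Day 1 anti-FXa and no Day 1 post-dose FX (Table 5.5-3). Their baseline FX still carries the same timing footnote and feeds the Month 3 comparison.
- The pre-study drug does not bear on anti-FXa from Week 2 on.

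**The case against.** The other side has several good points.

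- **Early sampling is permitted, not required.** A draw just before the first apixaban dose satisfies the footnote, and the same-day contrast is then fair even after VKA. This stands, but the protocol gives a site no reason to wait, and moves the other sample of the pair without it.
- **The analysis is described elsewhere.** Section 8.4.4 defers details to a separate population PK/PD plan that is not available here. Section 8.2 names prior thromboembolism and aspirin use as subgroups but leaves the list open. Prior anticoagulant use within 1 month is recorded (Section 3.4), as is screening INR. That plan may therefore already stratify or flag. This stands for the analysis side. It does not repair a baseline drawn at the wrong time, because sample timing is set in the protocol.
- **Odd Day 1 anti-FXa values are detectable.** In children 3 months or older, the LC-MSMS concentration comes from the same combined sample. This stands, and it is why flagging is practical.

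Two stronger readings are tempting. One is that either prior drug distorts both assays. The documents do not support this: VKA bears on baseline FX, whereas an anti-FXa assay with exogenous FXa gives no reason to expect a VKA effect, and nothing shows LMWH altering chromogenic FX. The other is that a pooled change in FX from baseline would be understated or reversed. No such summary is specified and the share of VKA switchers is unknown. In the 0.98 illustration a pooled mean cannot reverse. In the 1.87 illustration it reverses only if VKA switchers exceed about (1 - 0.70)/(1.87 - 0.70) = 26%.

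**Conclusion.** The concern holds in limited form. After VKA, baseline FX as scheduled can misstate both the endogenous level and apixaban's inhibition. After LMWH, the Day 1 anti-FXa reading in children 3 months or older may include LMWH activity. How large either effect is depends on FX suppression at the draw, the INR wait, the LMWH interval and the half-life. The documents give none of these, and the assumed ranges run from no bias to a reversed sign within a child.

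The FX conclusion rests on the assumption that VKA lowers FX. The LMWH conclusion rests on the protocol's own use of anti-Xa to monitor LMWH.

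This is a worthwhile improvement to a secondary objective in a descriptive study. It does not touch the primary bleeding endpoint or the PK concentrations, and it does not show that the PD analysis plan is wrong.

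**What to change.** 1. Amend the footnotes in synopsis Tables 1.1-1.4, Tables 5.5-1 to 5.5-4 and Appendix 1, and the FX row of Table 5.1-1. In VKA switchers whose first apixaban dose is deferred, the pre-dose FX sample should also be postponed, to just before that dose.
2. Record with the Day 1 samples the INR and the time of the last VKA, LMWH or UFH dose. UFH is included because Section 4.5 allows bridging with it; its effect on the assay is assumed to be like that of LMWH.
3. Summarise FX by prior anticoagulant (none, VKA, LMWH). For Month 3 and Month 6, do not treat the VKA switchers' baseline as endogenous FX: an INR just below 2 may still reflect VKA, so the timing change alone does not cure this comparison.
4. Flag Day 1 anti-FXa after recent LMWH or UFH and leave it out of the concentration/anti-FXa relation, at least in a sensitivity analysis. Week 2 to Month 6 samples can carry that relation.

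Cost: footnote edits, a few data fields and analysis-plan wording. No sample or visit is added, because the deferred post-dose draw already brings the child to a first-dose visit, and no dosing or switching rule changes. The downside is fewer children in any pooled baseline-change summary and in the Day 1 anti-FXa data.
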